4.2 Criteria for Starting Subsequent Cycles

A cycle may be repeated every 28 days if the patient has at least stable disease or progressive disease is ruled out based on clinical or laboratory evidence and met the clinical and laboratory parameters as defined by the guidelines for dose modification and toxicity management (Section 5) and does not have a dose limiting toxicity requiring permanent removal from protocol therapy (Section 5.1). A patient may resume protocol therapy at the same or a reduced dose if they have a toxicity that is adequately managed (eg: myelosuppression, hypertension, hepatotoxicity, electrolyte abnormality, bleeding, wound healing, etc) as outlined in Sections 5.2, 5.3, and 5.4.

4.3 Concomitant Therapy

If new data become available showing an interaction between a concomitant medication and pazopanib that is considered significant enough to impact the risk/benefit balance of pazopanib, the list of permitted/prohibited medications in the Investigator Brochure will be updated either during the annual update or within an IB supplement. Any such changes will be communicated to the site via a letter which should be stored in the site's study file.

4.4 **Permitted Medications**

All patients will be asked to provide a complete list of prescription and over-the-counter medications that have been taken within the previous 4 weeks prior to Screening. The investigator must be informed as soon as possible about any new medication(s) taken from the time of Screening until the completion of the post-treatment follow-up visit.

All concomitant medications taken during the study will be recorded in the eCRF with indication, dose information, and dates of administration.

Patients should receive full supportive care during the study, including transfusion of blood and blood products, treatment with antibiotics, analgesics, erythropoietin, or bisphosphonates, when appropriate.

Anti-emetics (such as prochlorperazine, lorazepam, ondansetron or other 5-HT3 antagonists) may be administered prophylactically in the event of nausea. However, it is important to note that 5-HT3 blockers that are given daily for a prolonged period of time may prolong QTc and should be used with caution. (Appendix IIIB). Anti-diarrheals, such as loperamide, may be administered as needed in the event of diarrhea. Although acetaminophen at doses of ≤ 2 g/day is permitted, it should be used with caution in patients with impaired liver function.

4.5 **Permitted Medications – Use with Caution**

4.5.1 Specific recommendations regarding anticoagulants:

Results from drug-drug interaction studies conducted in patients with cancer suggest

that pazopanib has no effect on the metabolism of S-warfarin. Hemorrhagic events, however, have been reported in clinical studies with pazopanib. Therefore, if the investigator decides to continue pazopanib and anticoagulants use concomitantly, it should be used with caution in patients with increased risk of severe bleeding or who are benefitting from treatment and require the initiation of concomitant anticoagulant therapy (e.g., warfarin or its derivatives, low molecular weight heparin, unfractionated heparin) while on study. Note: Patients are excluded from enrolling on the study if they are taking therapeutic doses of S-warfarin at the time of screening. Patients taking concomitant anticoagulant therapy should be monitored regularly for changes in relevant coagulation parameters as clinically indicated, as well as for any clinical bleeding episodes.

4.5.2 Specific recommendations regarding hypoglycemic therapy including insulin:

Results from drug-drug interaction studies conducted in patients with cancer suggest that there will be no clinically relevant pharmacokinetic interaction between pazopanib and hypoglycemic agents. Transient decreases in serum glucose (mainly Grade 1 and 2, rarely Grade 3) have been observed in clinical studies with pazopanib. In addition, decreases in blood sugar have been reported in patients treated with another small molecule tyrosine kinase inhibitor, sunitinib (British Journal of Cancer 2008: 99, 1380). Such changes may require an adjustment in the dose of hypoglycemic and/or insulin therapy. Patients should be advised to report symptoms of hypoglycemia (e.g., confusion, visual disturbances, palpitations, and sweating). Serum glucose should be tested during treatment with pazopanib as outlined in the protocol and as clinically indicated.

- 4.5.3 Concomitant use of pazopanib and simvastatin increases the risk of ALT elevations and should be undertaken with caution and close monitoring. If a patient receiving concomitant simvastatin develops ALT elevations, follow dosing guidelines for pazopanib or consider discontinuing simvastatin.
- 4.5.4 Concomitant administration of pazopanib with esomeprazole decreases the bioavailability of pazopanib by 40% (AUC and Cmax). Co-administration of pazopanib with Proton Pump Inhibitors (PPIs) should be avoided. Co-administration of pazopanib with PPIs is PROHIBITED from 24 hours before the first dose of pazopanib until after the final PK blood sample is collected on Day 15 ± 1 day of Cycle 1. After this, if the concomitant use of a proton-pump inhibitor (PPI) is medically necessary, it is recommended that the dose of pazopanib be taken without food once daily in the evening concomitantly with the PPI (Section 4.8). If the concomitant administration of an H2-receptor antagonist is medically necessary, pazopanib should be taken without food at least 2 hours before or at least 10 hours after a dose of an H2-receptor antagonist. Pazopanib should be administered at least 1 hour before or 2 hours after administration of short-acting antacids.
- 4.5.5 Concurrent Anti-Hypertensive Therapy: The algorithm in Section 5.4.1 will be used to grade and manage pazopanib related hypertension. Should initiation of anti-hypertensive therapy be required, single agent therapy (commonly including the calcium channel blockers amlodipine or nifedipine) may be started without notifying the study chair.

- 4.5.6 Anti-inflammatory and anti-platelet agents (e.g. aspirin, and/or ibuprofen, or other NSAIDs) could result in elevated blood pressure or increased bleeding episodes when co-administered with pazopanib and therefore should be used with caution.
- 4.5.7 Patients' medications should be reviewed at eligibility, before treatment initiation, and during treatment. Any concomitant medications that are "generally accepted" to cause a risk of Torsade de pointes are prohibited (see Appendix IIIB). Those "associated" with a risk of QTc prolongation and/or Torsades de pointes should be discontinued or replaced with drugs that do not carry these risks, if possible. Patients who must take these medications should be watched carefully for symptoms of QTc prolongation, such as syncope. Performing additional EKGs on patients who must take one or more of these medications is recommended but not required, at the investigator's discretion.

4.6 The Effects of Pazopanib on Other Drugs

In vitro data indicate that pazopanib is a potential inhibitor for CYP3A4, CYP2C8, CYP2D6, CYP1A2, CYP2C9, CYP2C19, CYP2A6, CYP2B6, and CYP2E1. Pregnane X receptor transient transfection assay suggested some potential for human CYP3A4 induction at high concentrations. Results from drug-drug interaction studies conducted in patients with cancer suggest that pazopanib is a weak inhibitor of CYP3A4, CYP2C8, and CYP2D6 in vivo, but had no clinically relevant effect on CYP1A2, CYP2C9 or CYP2C19 metabolism. Therefore, concomitant use of pazopanib with certain medications (substrates of CYP3A4, CYP2C8, and CYP2D6) with a narrow therapeutic window should be undertaken with CAUTION due to the potential for alterations in the pharmacologic effects of these medications or an increased risk for serious or life- threatening adverse events associated with such medications (see below) secondary to the inhibition of specific CYP enzymes by pazopanib. In addition, the potential for drug interaction with such medications, although diminished, may persist after the last dose of pazopanib due to its long half-life (i.e., mean 30.9 hours); therefore, continue to exercise CAUTION for at least 7 days and up to 15 days after the last dose of pazopanib when administering these medications. These medications include (but are not limited to):

- Ergot derivatives: dihydroergotamine, ergonovine, ergotamine, methylergonovine (potential increased risk for developing ergot toxicity that includes severe vasospasm leading to peripheral as well as cerebral ischemia)
- Neuroleptics: pimozide (potential increased risk for QT interval prolongation, ventricular arrhythmia, and sudden death)
- Antiarrhythmics: bepridil, flecainide, lidocaine, mexiletine, amiodarone, quinidine, propafenone (potential increased risk for QT interval prolongation and Torsade de Pointes)
- Immune modulators: cyclosporine, tacrolimus, sirolimus (potential increased risk for nephrotoxicity and neurotoxicity)
- Miscellaneous: quetiapine, risperidone, clozapine, atomoxetine.

4.7 The Effects of Other Drugs on Pazopanib

Results from *in vitro* studies suggest that the oxidative metabolism of pazopanib in human liver microsomes is mediated primarily by CYP3A4, with minor contributions from CYP1A2 and CYP2C8. Furthermore, *in vitro* data suggest that pazopanib is a substrate for P-glycoprotein and for breast cancer resistance protein. Substances that induce or inhibit CYP3A4 may alter the pharmacologic effects of pazopanib and should be used with **CAUTION**.

Medications that inhibit CYP3A4 may result in increased plasma pazopanib concentrations. Co-administration of strong CYP3A4 inhibitors is prohibited (see Section 4.8); therefore selection of an alternate concomitant medication with no or minimal potential to inhibit CYP3A4 is recommended.

Medications that induce CYP3A4 may result in decreased plasma pazopanib concentrations and a loss of efficacy and therefore are prohibited (See Section 4.8). Anticonvulsant drugs that do not induce CYP enzymes are allowed. Refer to Appendix IIIA for a list of anticonvulsant drugs with little or no enzyme induction. The use of azithromycin or fluconazole is discouraged but allowed.

4.8 **Prohibited Medications**

Patients should not receive other anti-cancer therapy [cytotoxic, biologic, radiation, or hormonal (other than leuprolide or other GnRH agonists)] while on treatment in this study. Medications that inhibit CYP3A4 may result in increased plasma pazopanib concentrations; therefore, co-administration of strong CYP3A4 inhibitors is **PROHIBITED** beginning **14** days prior to the first dose of protocol therapy until discontinuation of the protocol therapy. **Strong CYP3A4 inhibitors include (but are not limited to)**:

- Antibiotics: clarithromycin, telithromycin, troleandomycin, roxithromycin
- HIV protease inhibitors: ritonavir, indinavir, saquinavir, nelfinavir, amprenavir, lopinavir
- Antifungals: itraconzaole, ketoconazole, voriconazole
- Antidepressants: nefazodone

CYP3A4 inducers may decrease plasma pazopanib concentrations. Selection of an alternate concomitant medication with no or minimal enzyme induction potential is recommended. **Drugs that induce CYP3A4 and may decrease pazopanib plasma concentrations are PROHIBITED and include (but are not limited to)**:

- Glucocorticoids for greater than 2 weeks duration: cortisone (>50 mg/day), hydrocortisone (>40 mg/day), prednisone (>10 mg/day), methylprednisolone (>8 mg/day), dexamethasone (>1.5 mg/day)
- Anticonvulsants: phenytoin, carbamezepine, phenobarbital, oxcarbazepine, primidone, fosphenytoin
- HIV antivirals: efavirenz, nevirapine, tipranavir
- Antibiotics: rifampin (rifampicin), rifabutin, rifapentene
- Miscellaneous: St. John's Wort, modafinil, pioglitazone

Grapefruit or grapefruit juice is prohibited as it inhibits CYP3A4 activity and may also increase plasma concentrations of pazopanib.

As noted above, co-administration of pazopanib with PPIs should be avoided and is prohibited from 24 hours before the first dose of pazopanib until after the final PK blood sample is collected on Day 15 ± 1 day of Cycle 1.

The therapy delivery maps (TDMs) are on the next 2 pages.

4.9 Therapy Delivery Map (TDM) - Cycle 1

This therapy delivery map relates to Cycle 1: Pazopanib treatment given once daily continuously for 28 days.		
See Section 4.10 for the therapy delivery map for subsequent cycles. 1 cycle = 28 days. Dosing is continuous. There is no interruption between cycles.	Patient name/initials	DOB

Criteria to start Cycle 1 are described in Section 3.2. Extensive details are in Section 4.1 (treatment overview). Cycle 1 lasts 28 days.

DRUG	ROUTE	DOSAGE Circle applicable formulation and strikethrough unused formulation to avoid confusion	DAYS	IMPORTANT NOTES	OBSERVATIONS OBTAIN OTHER ASSESSMENTS AS REQUIRED FOR GOOD PATIENT CARE
Pazopanib (GW786034) IND# 065747	РО	If tablets: 450 mg/m ² /dose given once daily (Max dose: 800 mg) If powder in suspension: 225 mg/m ² /dose given once daily (Max dose: 400 mg)	1-28	Take on an empty stomach (at least 1 hour before a meal or 2 hours after a meal). See Section 4.1 for further details.	 a History, physical exam, vital signs, blood pressure b Urinalysis (including UPC) and/or 24 hour urine for protein c Ht, Wt, BSA, performance status d CBC, differential, platelets, electrolytes including K⁺, Ca⁺⁺, PO4,³⁻Mg, ⁺creatinine, total protein, albumin, ALT, bilirubin, amylase, lipase e PT/PTT/INR, pregnancy test, TSH f ECHO, EKG, plain x-ray of knee (see Section 7.2.1) g Disease evaluation including BMA/Bx, Urine VMA/HVA, AFP as indicated (see Section 7.1). h PK (see Section 7.3 & Appendix VI). i PD (see Sections 7.1 and 7.4)

Ht____kg

BSA m²

Date	Date	Week	Day	Pazopanib	Assessments	Comments (Include any held doses, or dose			
Due	Given			mg		modifications)			
Please refer to the Visit Schedule in Section 7 for Screening assessments.									
				Enter calculated dose ab	ove and then dose admin	nistered below			
		1	1	mg	a, b, c^1 , d^2 , h^3 , i^3				
			2	mg					
			3	mg					
			4	mg					
			5	mg					
			6	mg					
			7	mg					
		2	8	mg	a, d^2				
			9	mg					
			10	mg					
			11	mg					
			12	mg					
			13	mg					
			14	mg					
		3	15	mg	a, d^2, h^4				
			16	mg					
			17	mg					
			18	mg					
			19	mg					
			20	mg					
			21	mg					
		4	22	mg	a, d^2				
			23	mg					
			24	mg					
			25	mg					
			26	mg					
			27	mg					
			28	mg					
			See Section	See Section 4.2 for criteria for starting a subsequent cycle. See section 5 for dose modifications					

¹Evaluations obtained for screening will ONLY be repeated at Cycle 1 Day 1 if they are older than 7 days.

² If Grade 4 neutropenia or thrombocytopenia, CBCs should be checked at least twice a week (every 3 to 4 days) until ANC \geq 750/µL and platelets \geq

75,000/µL (transfusion independent).

³ Prior to the first dose

⁴Obtain at the same time as safety labs.

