In a randomized placebo-controlled Phase III study of pazopanib monotherapy in patients with soft tissue sarcoma [STS]), the median time on pazopanib was 19.4 weeks, as compared with 8.1 weeks in the placebo arm. The most common AEs ($\geq 20\%$) reported in the pazopanib arm (as of May 23, 2011) were fatigue (65%), diarrhea (59%), nausea (56%), weight decreased (51%), hypertension (42%), decreased appetite (40%), hair color changes (39%), vomiting (33%), tumor pain (30%), dysguesia (28%), headache (23%), musculoskeletal pain (23%), myalgia (23%), gastrointestinal pain (23%), and dyspnea (20%). Twenty-eight percent of patients on placebo and 63% of patients on pazopanib experienced an AE of maximum Grade 3 or higher. The proportion of patients who experienced maximum Grade 4 and Grade 5 AEs was similar in both treatment arms.³⁰

An analysis of integrated safety data from a Phase III study in patients with STS and a single arm Phase II study of pazopanib monotherapy in patients with STS showed a safety profile similar to that observed in the pazopanib arm of the Phase III study alone. Increased rates of myocardial dysfunction, venous thromboembolic events, and pneumothorax were newly observed in the STS studies as compared to RCC. Rare but severe AEs previously described for VEGFR inhibitors, such as cardiac/cerebral ischemia, hemorrhage, and bowel perforation, were observed with pazopanib treatment.

A review of SAEs across oncology studies revealed that the most frequently reported SAEs (\geq 70 events), regardless of causality and treatment regimen, as of September 9, 2011 in decreasing order of frequency were increased ALT, dyspnea, vomiting, abdominal pain, pyrexia, diarrhea, anemia, pneumonia, dehydration, and aspartate aminotransferase (AST) increased.

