3.1.5 Study Enrollment

Patients may be enrolled on the study once all eligibility requirements for the study have been met. Specific procedures related to the requirements for patient enrollment are described in protocol Section 3 and in the Study Procedures Manual. Sites will be required to complete a session into the (IWRS) to record patient information as described in Section 3.1.1.

3.1.6 Timing

Patients must be enrolled before treatment begins. The date protocol therapy is projected to start must be no later than 5 calendar days after the date of study enrollment. See Section 3.2 for timing requirements for eligibility studies. See Section 3.1.7 for timing requirements for baseline studies to be obtained prior to start of therapy. Note: Repeat laboratory and imaging studies may be required if enrollment and start of therapy do not occur on the same day.

3.1.7 Requirements to Initiate Protocol Therapy

3.1.7.1 Laboratory Studies: If more than 7 calendar days elapse between the date laboratory studies to determine eligibility were obtained

(Section 3.2.8) and the start date of treatment, then the following studies must be repeated prior to initiating protocol therapy: CBC with differential, bilirubin, ALT (SGPT) and serum creatinine. If any of these repeat laboratory assessments are outside the parameters required for eligibility (labs may again be repeated within 48-72 hours), then the patient is not eligible for protocol therapy.

Note: For hepatoblastoma patients, blood for serum alpha fetoprotein (AFP) must be drawn within 48 hours prior to initiating protocol therapy. It is not required that the results be known prior to enrollment.

- 3.1.7.2 Imaging Studies: Imaging studies must be performed within 14 calendar days prior to initiating protocol therapy. If more than 14 calendar days have elapsed between the date imaging studies to determine eligibility were obtained (Section 3.2) and the enrollment date, then repeat imaging assessments must be obtained prior to initiating protocol therapy.
- 3.1.7.3 Cardiac studies: Cardiac ECHO and electrocardiogram (ECG) must be performed within 14 calendar days prior to initiating protocol therapy. If more than 14 days have elapsed between the date cardiac studies to determine eligibility were obtained (Section 3.2.8.4) and the enrollment date, then repeat cardiac studies must be obtained prior to initiating protocol therapy.

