5.1 Definition of Dose Limiting Toxicity (DLT)

DLT will be defined as any of the following events that are at least possibly, probably, or definitely attributable to pazopanib. See Section 5.4 for the Potential Pazopanib Specific Side Effects. Dose-limiting hematological and non-hematological toxicities are defined differently.

5.1.1 Hematological Dose-Limiting Toxicity

- a) For patients who are evaluable for hematologic toxicity assessment (patients **without** bone marrow involvement)
 - Grade 4 Thrombocytopenia (platelet count < 25,000/mm3) or Grade 4 neutropenia
 - Any hematologic toxicity requiring dose reduction or treatment interruption for >14 days

b) For all patients:

- \geq Grade 2 arterial thromboembolic events (visceral arterial ischemia, peripheral ischemia, or ischemia cerebrovascular)
- Grade 3 or 4 venous thromboembolic event
- Any thrombotic event (other than central venous line [CVL] associated thrombosis) requiring systemic anticoagulation

5.1.2 Non-Hematological Dose-Limiting Toxicity

- 5.1.2.1 Any Grade 4 non-hematologic toxicity
- 5.1.2.2 Any Grade 3 non-hematological toxicity, with the specific exclusion of the following:
 - Grade 3 nausea and vomiting of less < 3 days duration
 - Grade 3 fever or infection,
 - Grade 3 hypophosphatemia, hypokalemia, hypocalcemia or hypomagnesemia responsive to oral supplementation within 7 days of start of supplement (see Section 5.4.4 for dose modifications)
- 5.1.2.3 Grade 2 allergic reactions that necessitate discontinuation of protocol therapy will not be considered a dose-limiting toxicity.
- 5.1.2.4 Any Grade 2 non-hematological toxicity that persists for \geq 7 days and is considered sufficiently medically significant or sufficiently intolerable by patients that it requires treatment interruption may also be considered a DLT following discussion with the Study chair and a Novartis Medical Lead.
- 5.1.2.5 Hypertension will be graded according to the NCI CTCAE; however, dose limiting hypertension will be considered as the following:

- Grade 4 hypertension
- A blood pressure >25 mmHg above the 95th percentile for age, height, and gender (see Appendix V) confirmed by repeated measurement on the same day (See Sections 5.4.1 and 4.1.5.1 for management)

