5.3 Dose Modifications for Non-Hematological Toxicity

Specific instructions for the management of potential pazopanib side effects are included in Section 5.4.

- 5.3.1 For any non-hematologic dose limiting toxicity as detailed in Section 5.1.2:
 - a) Pazopanib should be held
 - b) If the non-hematologic DLT is a pazopanib specific toxicity, the dosing guidelines in Section 5.4 should be followed
 - c) If the non-hematologic DLT returns to baseline within 14 days of holding pazopanib, subsequent doses of pazopanib should be given at a reduced dose.
 - If toxicity does not resolve to meet continued treatment parameters within 14 days of drug discontinuation, and if re-challenge is to be considered, the Study Chair must be contacted as outlined in Section 4.2 to discuss.
 - If DLT recurs in a patient who has resumed treatment after the maximum allowed dose reductions, the patient must be removed from protocol therapy, unless the patient has been approved for a further dose reduction following discussion with the Study Chair.

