Contact the Study Chair if you need further guidance or would like to discuss an event involving abdominal pain or bowel perforations.

5.4.3 Hepatotoxicity:

Adverse events & descriptions	Dose Modifications & Evaluations
Grade 1 ALT/AST elevation	1. Continue pazopanib at current dose
	2. Check liver function tests $(LFTs)^1$ as per
	Evaluations table in Section 7.1
Grade 2 ALT/AST elevation without	1. Continue pazopanib at current dose
bilirubin elevation (defined as total	2. Consider performing the following to exclude
bilirubin ² \leq 1.5 x ULN or direct bilirubin	hypersensitivity and other contributing factors:
\leq 35% of total bilirubin) and without	Eosinophil count
hypersensitivity symptoms (eg: fever,	• Viral serology ⁴ for hepatitis A, B and C
rash)	• Liver imaging (ultrasound)
	3. Monitor patient closely for clinical signs and
	symptoms
	4. Perform LFTs ¹ weekly (or more frequently if
	clinically indicated) until AST/ALT \leq Grade 1

	1	· · · · · · · · · · · · · · · · · · ·
≥Grade 3 ALT elevation without bilirubin elevation (defined as total bilirubin ² ≤ 1.5 x ULN or direct bilirubin ≤35% of total bilirubin) and without hypersensitivity symptoms (e.g., fever, rash)	L 1. 2. 3. 4. 5.	 iver Event Interruption/Stopping Criteria³: Hold pazopanib. Repeat LFTs¹ within 72 hrs to confirm ≥Grade 3 ALT elevation; if confirmed: Perform the following assessments to exclude hypersensitivity and other contributing factors: Eosinophil count Optional viral serology⁴ for hepatitis A, B, C and E, cytomegalovirus⁴, Epstein Barr virus⁴ (IgM antibody, heterophile antibody, or monospot testing) Liver imaging (Ultrasound) Monitor patient closely for clinical signs and symptoms Perform LFTs¹ weekly (or more frequently if clinically indicated) until ALT reduced to ≤ Grade 1 Pazopanib may be held for up to 14 days, if ALT returns to ≤ Grade 1 and patient is benefitting from treatment, pazopanib may be resumed at a reduced dose following Novartis / Study Chair approval (contact the Sponsor Medical Lead and the Study Chair via email or phone to start the approval process). If approval for retreatment is granted, the patient must be reconsented (with a separate informed consent) specific to hepatotoxicity. For patients on tablets dose reductions are as follows: If on 800 mg, then reduce to 400 mg daily If on 600 mg, then reduce to 400 mg

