7.1 Required Clinical, Laboratory and Disease Evaluations

See Section 3.2 and Section 3.3 for eligibility requirements. See Section 3.1.7 for requirements to initiate protocol therapy. Laboratory tests used to determine eligibility may be counted as the Week 1 studies if the tests were drawn within 7 days of treatment start and there have been no significant changes in the patient's clinical status (Section 3.1.7.1)

STUDIES TO BE OBTAINED	Pre- Study	During Cycle 1	Prior to Subsequent Cycles ¹	During Subsequent Cycles	End of Therapy ²	Survival Follow-up
History	X	Weekly	Х	Every other week for Cycles 2 & 3, then prior to each subsequent cycle	X	
Physical Exam, Vitals (including BP ³)	X	Weekly	Х	Every other week for Cycles 2 & 3, then prior to each subsequent cycle	Х	
Height, weight, BSA	Х	Cycle 1 Day 1^4	Х			
Performance Status	Х	Cycle 1 Day 1 ⁴	Х		Х	
CBC, differential, platelets	X	Weekly ^{5,6}	X	Weekly for Cycle 2; every other week for Cycle 3; then prior to each subsequent cycle	Х	
Electrolytes including K ⁺ , Ca ⁺⁺ (ionized Ca ⁺⁺), PO ₄ , MG ⁺⁺	X	Weekly	X	Weekly for Cycle 2; every other week for Cycle 3; then prior to each subsequent cycle	X	
Creatinine, ALT ⁷ , bilirubin, Amylase, Lipase	X	Weekly	X	Weekly for Cycle 2; every other week for Cycle 3; then prior to each subsequent cycle	X	

Obtain indicated studies prior to the start of cycle unless otherwise indicated.

Page 67 Protocol No. VEG116731

Total protein/albumin	Х	Weekly	X	Weekly for Cycle 2; every other week for Cycle 3: then prior to each subsequent cycle	Х	
TSH ⁸	Х		Prior to Cycle 3, 5, 8, 11 and every 3 rd cycle thereafter			
PT, PTT, and INR	Х		Prior to Cycle 3 and every 6 cycles thereafter			
Urinalysis (UPC and/or 24 hour urine for protein) ⁹	Х	Х	Х		Х	
Disease Evaluation ¹⁰ (including bone marrow aspirate/biopsy ¹¹)	X		Prior to Cycle 3, 5, 8, 11 and every 3 rd cycle thereafter ¹²		X	
Serum AFP (for hepatoblastoma patients only) ¹³	Х		Prior to Cycle 3, 5, 8, 11 and every 3 rd cycle thereafter ¹²		Х	
Urine VMA/HVA (for neuroblastoma patients only) ¹⁴	Х		Prior to Cycle 3, 5, 8, 11 and every 3 rd cycle thereafter ¹²		Х	
Serum Pregnancy Test ¹⁵	Х	-	Х	-		
Patient Diary		Х	X			
ECHO ¹⁶	Х		Prior to Cycle 2, 5 and then every 6 cycles			
EKG (including QTcB) ¹⁷	Х		Prior to Cycle 2, 5 and then every 6 cycles			
Plain radiograph of tibial growth plates ¹⁸	Х		Prior to Cycle 2, 5 and then every 6 cycles			
Pharmacokinetics ¹⁹		Х	Prior to every odd cycle			
Survival status ²⁰						Х

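### The visit schedules draw ALT and bilirubin but not AST or ALP, so an isolated AST rise has no scheduled test and AST/ALP summaries would rest largely on a selected subset

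*Protocol*

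**What the plan says.** **Scheduled chemistry.** Item d of the therapy delivery maps (Sections 4.9 and 4.10) lists "total protein, albumin, ALT, bilirubin, amylase, lipase". The evaluations table in Section 7.1 has a row of creatinine, ALT, "bilirubin, Amylase, Lipase". No row of that table names AST or ALP at pre-study, on treatment or at end of therapy. The panel repeated before first dose (Section 3.1.7.1) is "CBC with differential, bilirubin, ALT (SGPT) and serum creatinine". Liver eligibility (Section 3.2.8.3) sets limits for bilirubin, ALT and albumin only.

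**Text that acts on AST or ALP.**
- Section 5.4.3 grades ALT and AST together in its Grade 1 row and in the row that begins "Grade 2 ALT/AST elevation without" bilirubin elevation. The Grade 1 action sends the site to the "Evaluations table in Section 7.1".
- Section 5.1.2.2 counts as a DLT, if attributable, "Any Grade 3 non-hematological toxicity, with the specific" exclusion of short-lived nausea and vomiting, fever or infection, and correctable electrolyte disturbances. AST is not on that exclusion list.
- SAP Section 11.7.1 names total bilirubin, ALT, AST and ALP as the liver parameters of interest and uses all four in its Hy's law rule.

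**The only bridge.** Footnote 7 of Section 7.1, attached to ALT, refers a patient with an LFT elevation to Section 5.4.3. Footnote 1 there defines LFTs as AST, ALT, ALP, GGT and total bilirubin.

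**The concern.** The toxicity rules and the SAP presuppose AST and ALP values that the schedule does not produce routinely. This has two consequences.

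*Detection.* If AST rises while ALT and bilirubin stay normal, nothing in the schedule finds it unless the site orders AST on its own initiative. That includes a rise large enough to count under Section 5.1.2.2. AST is not a remote concern: the protocol's list of the most frequent SAEs across oncology studies (Section 2.3.2, at least 70 events each) ends with "pneumonia, dehydration, and aspartate aminotransferase (AST) increased". DLT counts also decide whether the 225 mg/m² suspension dose continues (two or more in six evaluable patients, Section 2.5).

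*Interpretation.* AST and ALP values that reach the database by the protocol's own route come from patients in whom another liver test was already raised. A summary of those values describes that group, not the safety population.

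**Working it through.** The plan states no figure to reproduce here. The check is a comparison of text plus a count of visits.

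**Step 1. Planned ALT and bilirubin draws, pre-study through Cycle 3** (Section 7.1 table; days from Sections 4.9 and 4.10):

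| Period | Draws |
|---|---|
| Pre-study | 1 |
| Cycle 1, Days 1, 8, 15, 22 | 4 |
| Cycle 2, weekly | 4 |
| Cycle 3, every other week | 2 |

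1 + 4 + 4 + 2 = 11. Section 7.1 lets eligibility tests within 7 days of treatment start count as Week 1, which gives 10. After that there is one draw per cycle and one at end of therapy. Draws at which AST or ALP is named: 0.

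**Step 2. Conditional full panels over the same period.** The Grade 1 row of 5.4.3 points back to 7.1 and can be read in two ways: 7.1 sets both timing and content (no AST), or footnote 1 sets the content and 7.1 only the timing. On the second reading:
- No LFT elevation: 0.
- Elevation first found on the Cycle 1 Day 8 sample: Days 15 and 22 (2) + Cycle 2 (4) + Cycle 3 (2) = 8.
- Patient enrolled with raised ALT: Section 3.2.8.3 admits ALT up to 2.5 × ULN, with ULN fixed at 45 U/L, so up to 2.5 × 45 = 112.5 U/L. Footnote 7 is not restricted to on-treatment values, so the panel could start on Day 1: 4 + 4 + 2 = 10, or 9 if the eligibility sample replaces Day 1.

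Under the Grade 2 and Grade 3 rows the LFTs are weekly whichever reading is taken. The isolated-bilirubin row asks for fractionation and, if the direct share is high, a search for the cause. It does not name AST or ALP.

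**Step 3. Baseline.** For a patient with normal screening ALT and bilirubin, no AST or ALP value is required before treatment on either reading. For a patient with raised ALT at entry, a Day 1 panel is possible on the second reading. It would qualify as baseline, since SAP Section 9.2.7 accepts values on the first dose date and Section 9.3.1 treats Day 1 laboratory tests as pre-therapy.

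**Step 4. What follows after an isolated Grade 3 AST rise.** Section 5.3.1 opens "For any non-hematologic dose limiting toxicity as detailed in Section 5.1.2" and under (a) holds pazopanib. Under (b), a pazopanib-specific toxicity follows Section 5.4. The hold row in 5.4.3 is triggered by ALT and the stop row by ALT with bilirubin or hypersensitivity; there is no AST-only hold row. The required action is therefore unclear.

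**Step 5. Use in the SAP.** Section 11.7 plans baseline-to-worst shift tables for biochemistry. Apart from worst-case results, its summaries use scheduled assessments only, and visit percentages count only subjects with a value. Under Section 9.2.8, change from baseline is missing if either value is missing. Applied to AST and ALP, these rules give results for whoever happened to be tested.

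**Step 6. What is not affected.** The Hy's law rule in SAP 11.7.1 needs AST or ALT above 3 × ULN with total bilirubin at least 2 × ULN, no baseline, and ALP below 3 × ULN or missing. Scheduled ALT and bilirubin are enough to find a case through ALT. Without ALP, a cholestatic picture cannot be ruled out.

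**Side check on blood counts.** Footnotes 5 and 6 of Section 7.1 end the extra CBCs at neutropenia Grade 3 or lower and thrombocytopenia Grade 2 or lower, with no transfusion condition. Section 5.2.1 and footnote 2 of Section 4.9 end them at ANC ≥ 750/µL and platelets ≥ 75,000/µL, transfusion independent. The stopping rules differ in the text.

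**The case against.** The strongest reply is that ALT-led monitoring is a coherent choice. ALT is the transaminase in eligibility, the pre-dose repeat, the 5.4.3 hold and stop rows and the protocol's own Hy's law SAE definition (Section 11.2), and the paediatric phase I liver events were ALT elevations (Section 2.4.1). The 5.4.3 rows that grade AST only continue the dose and repeat or consider tests. The SAP combines central and local data and admits unscheduled values to worst-case summaries. Sites may also order further tests for good care, and the contents of the central laboratory panel are not in these documents.

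Much of this stands, and it rules out several stronger readings that a reader might infer:
- *No one has a baseline AST or ALP.* Not supported: a patient enrolled with raised ALT might have a Day 1 panel (Step 3).
- *The schedule misses a mandatory hold.* Not supported: the action after an isolated Grade 3 AST rise is itself unclear (Step 4).
- *The SAP promises AST and ALP shift tables.* It promises them for biochemistry generally; AST and ALP are named only in 11.7.1.
- *AST rises alone often enough to be a hazard.* The list in Section 2.3.2 is regardless of causality and regimen, is headed by ALT, and does not say how many AST events came without an ALT rise.
- *Blood counts go unmonitored.* Section 5.2.1 covers all patients and ties restart to its own thresholds, so this is a wording conflict only.

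What the reply does not answer is the mismatch. If ALT alone was intended, the AST wording in 5.4.3 and the parameter list in SAP 11.7.1 should say so. Tests ordered at a site's discretion give neither a uniform baseline nor an unselected sample.

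**Conclusion.** The concern holds as a minor gap between the schedule, the toxicity rules and the SAP. AST and ALP are named at 0 of 11 planned chemistry draws through Cycle 3 and are reached only after another liver test rises, so an isolated AST rise has no scheduled test. Any AST or ALP summary would rest largely on a selected subset, and patients with normal screening ALT and bilirubin have no required baseline for it. No endpoint, sample size or error rate changes.

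The conclusion assumes that sites and the central laboratory followed the panel as printed. If AST and ALP were in fact run routinely, the selection would not arise and only the text would need correcting. The upper count of 10 conditional panels rests on reading 5.4.3 footnote 1 as setting the panel and on a raised ALT at entry. How often AST would rise alone cannot be estimated from these documents.

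**What to change.** **Preferred.** Add AST and ALP to the chemistry line of Sections 7.1, 4.9 and 4.10 wherever ALT is drawn, including pre-study and end of therapy. The cost is two assays on blood already taken and a few more laboratory abnormalities to review, with no new visit or procedure.

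**Failing that.** Limit the Grade 1 and 2 rows of Section 5.4.3 to ALT, and state in SAP Section 11.7.1 that AST and ALP are event-driven, so that their summaries describe patients who were tested. This costs wording only. Because SAP Section 4.3 records the decision to terminate the study, a schedule change cannot recover values that were not drawn. For the final report, the label is the part that can still be applied.

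**Secondary wording alignment.** Set the stopping points in footnotes 5 and 6 of Section 7.1 to those of Section 5.2.1 (for platelets, no transfusion in the preceding 7 days), and keep footnote 6's earlier Grade 3 platelet trigger.
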